**Early diagnosis of anastomotic leakage after colorectal surgery: a prospective observational validation study of the Dutch Leakage score, serum procalcitonin and serum CRP: the Italian ColoRectal Anastomotic Leakage (iCRAL) study group.**

**BACKGROUND**

Anastomotic leakage is a dreaded major complication after colorectal surgery [1]. The overall incidence of anastomotic dehiscence and subsequent leaks is 2 to 7 percent when performed by experienced surgeons [2-5]. The lowest leak rates are found with ileocolic anastomoses (1 to 3 percent) and the highest occur with coloanal anastomosis (10 to 20 percent) [6]. Leaks usually become apparent between five and seven days postoperatively. Almost half of all leaks occur after the patient has been discharged, and up to 12 percent occur after postoperative day 30 [4]. Late leaks often present insidiously with low-grade fever, prolonged ileus, and nonspecific symptoms attributable to other postoperative infectious complications. Small, contained leaks present later in the clinical course and may be difficult to distinguish from postoperative abscesses by radiologic imaging, making the diagnosis uncertain and underreported.

There is no uniform definition of an anastomotic dehiscence and leak [5]. In a review of 97 studies, as an example, 56 different definitions of an anastomotic leak were used [7]. The majority of reports define an anastomotic leak using clinical signs, radiographic findings, and intraoperative findings [8, 9]. The clinical signs include: Pain, Fever, Tachycardia, Peritonitis, Feculent drainage, Purulent drainage. The radiographic signs include: Fluid collections, Gas containing collections. The intraoperative findings include: Gross enteric spillage, Anastomotic disruption.

Risk factors for a dehiscence and leak are classified according to the site of the anastomosis (extraperitoneal or intraperitoneal). A prospective review of 1598 patients undergoing 1639 anastomotic procedures for benign or malignant colorectal disease found a significantly increased

risk of anastomotic leak with extraperitoneal compared with intraperitoneal anastomoses (6.6 versus 1.5 percent; 2.4 percent overall) [10].

Major risk factors for an extraperitoneal anastomotic leak include: The distance of the anastomosis from the anal verge (Patients with a low anterior resection and an anastomosis within 5 cm from the anal verge are the highest risk group for an anastomotic leak), Anastomotic ischemia, Male gender, Obesity.

Major risk factors for an intraperitoneal anastomotic leak include: American Society of Anesthesiologists (ASA) score Grade III to V, Emergent surgery, Prolonged operative time, Hand-sewn ileocolic anastomosis.

Controversial, inconclusive, or pertinent negative associations between the following variables and an anastomotic leak have been reported: Neoadjuvant radiation therapy, Drains, Protective stoma, Hand-sewn colorectal anastomosis, Laparoscopic procedure, Mechanical bowel preparation, Nutritional status, Perioperative corticosteroids.

Early diagnosis is crucial to treat patients limiting the related mortality. For this reason several clinical items were proposed in literature to detect anastomotic leakage as soon as possible: fever, pain, tachycardia, peritoneal, purulent or faecal drain, and dynamic ileus [1- 5]. Moreover, also laboratory markers were proposed, such as leukocytosis, serum procalcitonin (PCT) and C-Reactive Protein (CRP) [11-13]. Finally, in 2009 den Dulk et al. [14] proposed a leakage score (DUtch LeaKage, DULK), that consider several items (fever, heart rate, respiratory rate, urinary production, mental status, clinical conditions, signs of ileus, gastric retention, fascial dehiscence, abdominal pain, wound pain, leukocytosis, CRP, increase of urea or creatinine and nutrition status), to give a score, based on which is chosen a therapeutic strategy.

Therefore, we planned this study to prospectively evaluate anastomotic leakage rate after colorectal resections, trying to give a definite answer to the need for clear risk factors, and testing the diagnostic yield of DULK score and laboratory markers.

## **METHODS**

Prospective enrollment from September 2017 to November 2018 in 20 Italian surgical centers. All patients undergoing elective colorectal surgery with anastomosis will be included in a prospective database after having provided a written informed consent. A total of more than 1,160 patients is expected based on a mean of 50 cases/year per center.

### **Inclusion criteria**

1. Patients submitted to laparoscopic/open/converted ileo-colo-rectal resection with anastomosis (both intra- and extra-corporeal), including planned Hartmann's reversals.
2. American Society of Anesthesiologists' (ASA) class I, II or III
3. Elective surgery
4. Patients' written acceptance to be included in the study.

### **Exclusion criteria**

1. American Society of Anesthesiologists' (ASA) class IV-V
2. Patients with stoma before or at operation
3. Simple stoma closure
4. Transanal procedure
5. Pregnancy
6. Ongoing infection prior to surgery
7. Hyperthermic intraperitoneal chemotherapy for carcinomatosis.

### **Outcome measures**

1. Preoperative risk factors of anastomotic leakage (age, gender, obesity, state of nutrition [9-10], diabetes, cardiovascular, renal failure, inflammatory bowel disease, ASA class I-II vs III)

2. Operative parameters (approach, procedure, anastomotic technique, time of operation, pTNM stage)
3. Leukocyte count, serum CRP, serum procalcitonin and DULK score assessment in 2nd and 3rd postoperative day. Minor and major complications according to Clavien-Dindo classification [15, 16]
4. Anastomotic leakage rate
5. Morbidity-Mortality rates
6. Length of postoperative hospital stay

#### **Recorded data and follow-up**

Potential patient-specific and intraoperative risk factors will be recorded: gender, body mass index, nutritional status according to the Mini Nutritional Assessment short-form [17, 18], surgical indication (cancer, polyps, chronic inflammatory bowel disease, diverticular disease), preoperative albuminemia, use of steroids, renal failure and dialysis, preoperative leukocyte count, CRP, PCT cardiovascular or respiratory disease, American Society of Anesthesia score, bowel preparation (decision made by operating surgeon), laparoscopy or laparotomy, level of anastomosis and technique (mechanical or hand-sewn, intra- or extra-corporeal), operative time, presence of drainage, surgeon and perioperative blood transfusion(s). During the postoperative period, patients will be examined by the attending surgeon daily. Fever (central temperature > 38 °C), pulse, abdominal signs, bowel movements, volume and aspect of drainage (if present) will be recorded daily. Leucocyte count, CRP, PCT and Dulk score will be measured in the evening before the operation (in addition to albuminemia) and on postoperative days 2, 3, and 6 (optional). The attending surgeon will make any decision for complementary exams and imaging according to his own criteria. The rate of any complication will be calculated and graded according to Clavien-ALL 3 – Protocollo dello Studio

Dindo [15, 16] including all leaks (independently of clinical significance), wound infection, pneumonia, central line infection, urinary tract infection. Urinary tract infection will be diagnosed on the basis of positive urine culture with bacterial count. Central line infection will be diagnosed on the basis of positive blood culture. Superficial and deep incisional infections will be diagnosed according to the definitions of the Centers for Disease Control and Prevention and a culture will be performed [19]. Pneumonia will be diagnosed on the basis of clinical symptoms, and physical and radiological examinations. The surgeons will be blinded to the results of the CRP and PCT assays. Patients will be followed-up in the outpatient clinic up to 6 weeks after discharge from the hospital.

Main outcome is anastomotic dehiscence (intended as any deviation from the planned postoperative course related to the anastomosis, or presence of pus or enteric contents within the drains, presence of abdominal or pelvic collection in the area of the anastomosis on postoperative CT scan, performed at the discretion of the attending surgeon, leakage of contrast through the anastomosis during enema or evident anastomotic dehiscence at reoperation for postoperative peritonitis). Thus, all detected leaks will be considered independently of clinical significance. No imaging will be performed routinely in order to search for leakage.

Secondary outcomes are morbidity and mortality rates, and postoperative length of stay. All data will be prospectively recorded into CRF and transmitted to the coordinating center on a monthly basis. Thereafter, all data will be incorporated into a spreadsheet (MS Excel), checking for any discrepancy, that will be addressed and solved through strict cooperation between chief investigator, data manager and participating center.

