Appendix 1 **DULK SCORE [14]**

	Valori Normali	Score	Valori alterati	Score
Febbre	$\leq 38.0^{\circ} \text{C}$	0	$\geq 38.0^{\circ} \text{C}$	1
Frequenza cardiaca	$\leq 100 \text{ bpm}$	0	$\geq 100 \text{ bpm}$	1
Frequenza respiratoria	$\leq 30 \text{ atti/min}$	0	$\geq 30 \text{ atti/min}$	1
Diuresi	$\geq 30 \text{ ml/h o } 700 \text{ ml/die}$	0	$\leq 30 \text{ ml/h o } 700 \text{ ml/die}$	1
Stato mentale	Normale stato mentale	0	Agitazione o Letargia	2
Condizioni cliniche	Stabili o in miglioramento	0	Deterioramento	2
Segni di ileo	No	0	Ileo	2
Ritenzione gastrica	No	0	Ritenzione Gastrica	2
Deiscenza della fascia	No	0	Deiscenza della fascia	2
Dolore addominale o altri non di ferita	No dolore	0	Dolore non della ferita	2
Segni di infezione	No aumento leucociti o PCR	0	Aumento dei leucociti di $\geq 5\%$ o della PCR	1
Funzionalità renale	No aumento Urea o Creatinina	0	Aumento di Urea o Creatinina di $\geq 5\%$	1
Stato nutrizionale	Dieta Normale	0	Enterale/Parenterale Totale	1/2
TOTALE				

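### One DULK row can need the CRP result that surgeons are blinded to, no scorer is named, and four Appendix 1 limits fall in both columns

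*Protocol*

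**What the plan says.** Under Recorded data and follow-up, the Protocol sets the blind without exception: "The surgeons will be blinded to the results of the CRP and PCT assays". Leucocyte counts are not covered by it. The same section says "Leucocyte count, CRP, PCT and Dulk score will be measured in the evening before the operation" and repeats these measurements on postoperative days 2, 3 and, optionally, 6. It does not say who scores DULK. On examination after surgery it says that "patients will be examined by the attending surgeon daily", and it leaves further tests and imaging to that surgeon's judgement.

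In Appendix 1 the infection row gives 1 point for "Aumento dei leucociti di $\geq 5\%$ o della PCR" and 0 points for "No aumento leucociti o PCR". PCR is the Italian abbreviation for C-reactive protein, and the Background also lists CRP among the DULK items.

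The main outcome, defined later in the section, counts a collection near the anastomosis on a CT scan done at the attending surgeon's discretion. Routine imaging to look for leaks is excluded. On data flow the Protocol says: "All data will be prospectively recorded into CRF and transmitted to the coordinating center on a monthly basis".

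**The concern.** DULK, CRP and procalcitonin are the three tests named in the study title. The Statistical Analysis section compares their means by group and plans ROC areas. The blind keeps the CRP and procalcitonin results from influencing who is investigated for a leak. That protection matters here because the outcome depends partly on imaging that the attending surgeon chooses to order. A surgeon who learns that CRP has risen may be more likely to request the scan that finds the collection. CRP would then be judged against an outcome it helped to detect.

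One of the three tests contains another. Unless the Protocol says who fills in the CRP-dependent row and who sees the total, the score sheet offers a route around the blind. The alternative is that centres leave the row blank or score it on leucocytes alone, so that DULK is not the same score in all 20 centres. Limits that fall in both columns add a smaller source of inconsistency between centres.

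**Working it through.** **1. Weight of the row.** Maximum points in Appendix 1: fever 1 + heart rate 1 + respiratory rate 1 + urine 1 + six two-point items (12) + infection 1 + renal 1 + nutrition 2 = 20. The infection row is 1 of 20.

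**2. Can the row be scored without CRP?**
- Leucocytes up by at least 5%: the row is 1 whatever CRP does.
- Leucocytes not up: the row is 0 or 1 according to CRP, so it is undetermined while CRP is withheld.

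Surgeons may see leucocyte counts. A 1 in this row without a leucocyte rise therefore tells the surgeon that CRP rose.

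**3. How often this arises.** The Protocol gives no rates, so these are assumptions.
- Leucocyte rise in 50–90% of patients: CRP decides the row in 1 − 0.9 = 10% to 1 − 0.5 = 50%. Of the planned 1,062 that is 106 to 531 on each scoring day.
- CRP rise in 60–95%, independent of leucocytes: scoring on leucocytes alone lowers the total by 1 point in 0.1 × 0.6 = 6% to 0.5 × 0.95 = 47.5%. At 70% and 80% it is 0.3 × 0.8 = 24%.
- With a tetrachoric correlation of 0.5 the range is 2.4% to 45.6%.

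**4. Limits as printed in Appendix 1.** Testing each limit against both columns:
- Temperature 38.0 °C: meets the 0-point and the 1-point condition. The main text defines fever as strictly above 38 °C, unlike the 1-point column.
- Heart rate 100 bpm: meets both.
- Respiratory rate 30/min: meets both.
- Urine 30 ml/h or 700 ml/day: meets both. The two limits also differ, since 30 × 24 = 720 ml/day against 700.

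If a share q of readings in each row falls exactly on the limit (assumed 0.5%, 1% or 2%, independent rows), the share of patients with at least one such reading is 1 − (1 − q)^4 = 2.0%, 3.9% or 7.8%.

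**5. Effect on the DULK AUC.** This was computed by exact convolution of independent items under illustrative frequencies (non-leak/leak): fever .10/.30, heart rate .10/.30, respiratory rate .03/.10, urine .05/.12, renal .15/.30, mental state .04/.12, deterioration .05/.25, ileus .12/.30, gastric retention .08/.20, fascia .005/.02, pain .12/.35, nutrition 1 point .10/.20 and 2 points .05/.12. Odds ratios for leak were 1–3 for a leucocyte rise and 1–4 for a CRP rise, with correlation 0–0.5 between the two.
- AUC without the infection row: 0.832.
- Full row minus leucocytes-only row: −0.016 to +0.019.
- On-limit readings all scored 1 rather than all scored 0: a change of at most 0.002.

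For scale, the Hanley–McNeil standard error at n = 1,062 and AUC 0.75 is 0.062, 0.039 or 0.034 with 21, 53 or 74 leaks (2%, 5%, 7%). The 95% half-widths (1.96 × SE) are 0.12, 0.08 and 0.07. At AUC 0.832 they are 0.11, 0.07 and 0.06.

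**The case against.** The strongest reply is that the Protocol never assigns DULK to the surgeon. The scoring sentence is passive and groups DULK with laboratory assays, and the Protocol mentions a data manager and a coordinating centre. An unblinded person could complete the row. The row is also a single either/or point: a 1 gives no CRP level and says nothing about procalcitonin, and if CRP rises in most patients, learning that it rose adds little. All of this stands. It limits the point to a conditional one but does not remove it, because the Protocol nowhere says that someone other than a surgeon scores the row or that the total is withheld.

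On the limits, the text was read from a PDF, so a misread sign cannot be excluded, although the same pattern in all four rows makes this less likely. The urine discrepancy may be rounding. The infection-row problem depends on none of the overlapping signs.

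A reader might go further on two details, and the text does not support either:
- The 0-point entries "No aumento leucociti o PCR" and "No aumento Urea o Creatinina" might seem to leave a leucocyte, urea or creatinine rise of less than 5% without a score. The columns are headed as normal and altered values, so the ordinary reading is that a rise short of the altered limit scores 0.
- The Background lists wound pain as a DULK item, while Appendix 1 counts only pain that is not from the wound. The Background describes a published score; Appendix 1 is the sheet used for scoring.

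**Conclusion.** The point holds in conditional form. When leucocytes have not risen, the DULK infection row needs a result that surgeons must not see, and the Protocol does not say who completes it. If a surgeon scores the row or sees a total that includes it, the blind is partly broken; if CRP is withheld from the scorer, the row is incomplete. A reader might infer that the Protocol breaks its own blind in every case. It does not say that, because no scorer is named.

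The four overlapping limits, the differing fever definition and the mismatched urine limits are contradictions as printed. A reader might infer a material bias in the DULK AUC, but the figures do not support that: at most 0.002 from the limits, and within about ±0.02 from dropping CRP in every centre, against half-widths of 0.06 to 0.12. All of these AUC figures, and the 10–50% of patients affected, rest on assumed rates. The reason to act is to protect the blind, given that the surgeon controls the imaging behind the outcome, and to have one scoring rule across 20 centres. It should be changed, and the change is inexpensive.

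**What to change.** - State in Recorded data and follow-up that centres enter the bedside DULK items and the raw values on the CRF, with CRP and procalcitonin entered by someone other than the surgeons. The coordinating centre completes the CRP-dependent row and the DULK total from the laboratory values after follow-up.
- Reconcile the Appendix 1 limits with each other and with the fever definition in the main text, including the two urine limits. Apply one written rule centrally to the raw values. No cut-off is proposed here.
- Optionally, report the DULK AUC with and without the infection row, since that row contains CRP.

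The cost is small: CRF and appendix wording. Data already go to the coordinating centre monthly, and no extra patients or tests are needed. The downside is that the DULK total is not available at the bedside during the study. If the sponsor wants it there, the Protocol should instead name an unblinded scorer and say what the surgeon is shown, accepting that a total containing the row can partly reveal CRP.

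### Leak detection depends partly on surgeons who see most DULK items but not CRP or PCT, which can flatter DULK against the two serum markers by an amount the protocol does not fix

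*Protocol*

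**What the plan says.** The title presents the study as a validation of DULK, procalcitonin and CRP, and the Background gives one aim as "testing the diagnostic yield of DULK score and laboratory markers". The Statistical Analysis section plans ROC areas. It specifies no formal test of one index test against another.

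The section Recorded data and follow-up sets out who sees what:

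- "The surgeons will be blinded to the results of the CRP and PCT assays". No blinding to DULK, its clinical items or the leucocyte count is stated.
- "During the postoperative period, patients will be examined by the attending surgeon daily". Besides fever, "pulse, abdominal signs, bowel movements, volume and aspect of drainage (if present) will be recorded daily".
- "The attending surgeon will make any decision for complementary exams and imaging according to his own criteria".

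The main outcome, defined in the same section, has several components: a departure from the expected recovery attributed to the anastomosis, pus or bowel contents in a drain, a collection near the anastomosis on CT, contrast leak on enema, and dehiscence seen at reoperation for peritonitis. The CT is "performed at the discretion of the attending surgeon", and "No imaging will be performed routinely in order to search for leakage". What counts is what is found: "all detected leaks will be considered independently of clinical significance".

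In Appendix 1, most DULK lines are bedside observations (temperature, heart rate, ileus, non-wound pain, clinical deterioration and so on). One line concerns a rise in leucocytes or CRP, and one concerns renal function.

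**The concern.** In an accuracy study, the effort spent looking for the disease should not depend on one of the tests being judged. Here it can. The surgeon who decides on CT or enema has most of the DULK content in view and has neither CRP nor PCT. Two patients with the same contained leak and no other qualifying sign may then be classified differently: the one with a high DULK score is imaged and counted as a leak, while the one with a low score is not imaged and is analysed as a non-leak. This is differential verification.

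The outcome component based on an abnormal recovery pushes the same way. It is a clinical judgement assigned to no blinded assessor, and it overlaps DULK items such as ileus and deterioration.

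Blinding protects the CRP and PCT estimates from this mechanism, except where those markers correlate with DULK. Nothing comparable protects DULK. The Background itself says that small contained leaks are hard to diagnose and underreported, and these are the leaks affected. At stake is how the three ROC areas are read side by side.

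**Working it through.** The protocol gives no figure to reproduce. Two checks show the direction and plausible size. Every input below is an assumption unless a source is named.

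**1. Sensitivity.** Treat each test as positive or negative. Let *s* be the true sensitivity of both DULK and CRP (0.60), *c* the share of leaks that are contained and found only if imaged, and *p1* and *p0* the imaging probabilities when DULK is high or low. All other leaks are found.

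- Detected leaks with high DULK: A = s(1 − c + c·p1)
- Detected leaks with low DULK: B = (1 − s)(1 − c + c·p0)
- Apparent DULK sensitivity = A / (A + B)
- Apparent CRP sensitivity = (A·q1 + B·q0) / (A + B), where q1 and q0 are the probabilities of a positive CRP in leaks with high and low DULK.

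Independence means q1 = q0 = 0.60, so CRP stays at 60%. For correlation, take q1 = 0.75 and q0 = 0.375. Marginal CRP sensitivity is still 0.6 × 0.75 + 0.4 × 0.375 = 0.60.

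Example with c = 0.4 and imaging 80%/20%: A = 0.6 × (0.6 + 0.32) = 0.552 and B = 0.4 × (0.6 + 0.08) = 0.272. DULK is 0.552/0.824 = 67.0%. Correlated CRP is (0.552 × 0.75 + 0.272 × 0.375)/0.824 = 0.516/0.824 = 62.6%.

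| c | Imaging, high/low DULK | A | B | DULK | Gap, independent | CRP if correlated | Gap, correlated |
|---|---|---|---|---|---|---|---|
| 0.4 | 50%/40% | 0.480 | 0.304 | 61.2% | 1.2 | 60.5% | 0.8 |
| 0.3 | 60%/30% | 0.528 | 0.316 | 62.6% | 2.6 | 61.0% | 1.6 |
| 0.4 | 80%/20% | 0.552 | 0.272 | 67.0% | 7.0 | 62.6% | 4.4 |
| 0.5 | 90%/10% | 0.570 | 0.220 | 72.2% | 12.2 | 64.6% | 7.6 |

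Gaps are in percentage points. If p1 = p0, the formula returns s and the gap is zero.

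**2. ROC area.** A simulation of 1,000,000 patients per scenario gave DULK and one serum marker equal true areas (0.70 or 0.80). Leak prevalence was 2% or 7%, the ends of the range quoted in the Background. Correlation within leak status was 0, 0.3 or 0.6, and 70% of leaks were detected. Detection was either unrelated to DULK or logistic in DULK with slope 1 or 2 per standard deviation.

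| True area | Apparent DULK | Apparent marker | Gap |
|---|---|---|---|
| 0.80, detection depends on DULK | 0.85–0.89 | 0.79–0.85 | +0.02 to +0.09 |
| 0.70, detection depends on DULK | 0.77–0.81 | 0.70–0.76 | +0.03 to +0.11 |
| Either, detection unrelated to DULK | – | – | −0.003 to +0.004 |

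The gap was largest at zero correlation and smallest at 0.6, but stayed positive in every scenario where detection depended on DULK.

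**The case against.** Several objections have force.

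- **Imaging is not the only route.** A reader might infer that a contained leak counts only if a CT or enema is ordered. The outcome definition does not say so: drain contents and clinical deviation also qualify, and outpatient follow-up to 6 weeks after discharge can reveal later leaks. The mechanism bites fully only on contained leaks with no other qualifying sign.
- **Timing.** DULK is scored on postoperative days 2 and 3, with day 6 optional. The Background says leaks usually become apparent on days 5 to 7 and almost half after discharge. Many imaging decisions will therefore follow later signs rather than the score under test. Nothing in the document supports an 80%/20% split, and a weak dependence such as 50%/40% leaves about 1 point.
- **Correlation.** DULK itself includes a line for raised leucocytes or CRP, so exact independence is implausible and CRP shares some of the inflation.
- **Visibility of DULK.** The protocol does not say who computes the score. The daily list omits some items, and a surgeon blinded to CRP may be unable to complete the infection line. That the surgeon sees most bedside items is an inference, though a strong one from the daily examination and the item list.
- **No superiority test is planned.** True, but areas reported side by side for three tests named in the title will be ranked by readers.
- **Analysis detail may sit elsewhere.** A restricted-outcome analysis could be in an SAP that is not shown. Blinding, verification and outcome definition, however, are fixed in the protocol, and an analysis by imaging trigger is possible only if the trigger was recorded.

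These points reduce the size of the concern and make it uncertain, but they do not remove its direction.

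**Conclusion.** The concern holds in a limited form. As written, the plan lets detection of the less overt leaks depend on bedside signs that DULK scores, while shielding it from CRP and PCT. This can inflate DULK's apparent sensitivity and ROC area relative to the markers.

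With true sensitivity 60% for both tests and 30–50% of leaks contained, the spurious advantage is about 1 point under weak dependence, 4–7 points with imaging at 80%/20% (correlated or independent), and about 12 points at the extreme with independence. The documents fix none of the contained share, the imaging split or the correlation, so no single figure should be quoted as the bias.

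Two stronger readings are not supported. The blinding to CRP and PCT is not the error: it protects those estimates, and the weakness is the asymmetry combined with discretionary verification. Nor does the point show that any DULK advantage will be false, only that the design as described could not tell a real advantage from one created by the way leaks were found.

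**What to change.** In Recorded data and follow-up and in Statistical Analysis:

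1. Record on the CRF the date and trigger of every postoperative CT or enema, and report imaging rates by DULK level on days 2 and 3. The protocol's list of recorded data does not name this item; the CRF itself is not shown.
2. Report the ROC areas for DULK, CRP and PCT for the main outcome and, in parallel, for overt leaks: dehiscence at reoperation, or pus or bowel contents in a drain. Say that this reduces the bias without removing it, because reoperation also follows bedside signs and not every patient has a drain.
3. State that non-leak patients who were not imaged were not verified.
4. State that any ranking of DULK against CRP or PCT seen only with the main outcome is to be read as possibly due to differential verification.

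The cost is one CRF item and some wording, with no added imaging and no change to patient care. The overt-leak analysis will have fewer events and wider confidence intervals, and agreement between the two analyses will be reassuring but not proof that bias is absent.

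### Drain contents alone can establish the main outcome while having a drain is a candidate risk factor for it, so the drain odds ratio is likely, though not certain, to be biased upward

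*Protocol*

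**What the plan says.** All of the following is in the protocol.

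- **Outcome.** Recorded data and follow-up defines the main outcome by a list joined with "or". The drain item reads "presence of pus or enteric contents within the drains". No confirmation by imaging or reoperation is asked for. The other items are a departure from the expected recovery that is related to the anastomosis, a collection near the anastomosis on CT, contrast leaking during an enema, and dehiscence seen at reoperation.
- **Threshold and search.** The section states that "all detected leaks will be considered independently of clinical significance". It rules out routine imaging to look for leaks and leaves CT to the attending surgeon.
- **Exposure.** Under the statement "Potential patient-specific and intraoperative risk factors will be recorded", the list includes whether a drain is present. Drains are not universal: "volume and aspect of drainage (if present) will be recorded daily".
- **Analysis.** Statistical Analysis plans univariate and multivariate (logistic) analysis of risk factors for leakage, giving odds ratios with 95% confidence intervals.
- **Aim.** Background introduces a list with "Controversial, inconclusive, or pertinent negative associations between the following variables and an anastomotic leak have been reported". Drains are on that list, and the study sets out to settle which risk factors are clear.

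**The concern.** A patient with a drain can be counted as a leak in one more way than a patient without one. A small contained leak becomes countable once the effluent changes. Without a drain, the same leak counts only if it alters recovery, prompts a discretionary scan or enema, or is found at reoperation. Background itself describes small contained leaks as hard to diagnose and under-reported, so it is unsafe to assume that every leak surfaces by another route.

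This is differential ascertainment: the exposure forms part of how the outcome is observed. Adding covariates to a logistic model does not remove it. At stake is the interpretation of one odds ratio, for a factor the protocol itself calls unsettled. An apparent harm of drains could be nothing more than better detection.

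**Working it through.** The plan gives no figure on this point, so there is none to reproduce. The overlap follows from the text. The arithmetic shows only how large the bias could be if drains had no true effect.

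**Inputs.** From the protocol: leak incidence 2% to 7% (Background), N = 1,062 (Sample size; derived there for the ASA odds ratio and borrowed here only as a study size), two-sided level 0.05. Assumed, because the protocol does not give them: the share *o* of leaks found by the other criteria, the share *x* of the remaining leaks that a drain reveals, and the proportion of patients with a drain.

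**Step 1: apparent odds ratio under no effect.** Let the true risk be *p* in both groups, with *o* equal in both.

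- Observed risk without a drain: *p·o*
- Observed risk with a drain: *p·(o + (1 − o)·x)*

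Example with *p* = 0.05, *o* = 0.75, *x* = 0.8:

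- With a drain: 0.05 × 0.95 = 0.0475, odds 0.0475/0.9525 = 0.0499
- Without: 0.05 × 0.75 = 0.0375, odds 0.0375/0.9625 = 0.0390
- Odds ratio: 1.28

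| Found by other criteria (*o*) | OR at *x* = 0.3 | OR at *x* = 0.8 |
|---|---|---|
| 90% | 1.03 | 1.09 |
| 75% | 1.10 | 1.28 |
| 60% | 1.21 | 1.56 |

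The leak rate hardly matters. With *x* = 0.5 and *p* from 2% to 7%, the OR is 1.03 at *o* = 95%, 1.06 at 90%, 1.13 at 80%, 1.22 to 1.23 at 70% and 1.51 to 1.53 at 50%.

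**Step 2: chance of a falsely significant harmful result.** Two-proportion normal approximation, N = 1,062, *x* = 0.5, 50% or 80% of patients drained, *p* from 2% to 7%. The nominal value in the harmful direction is 2.5%. It becomes 2.7% to 4.2% when *o* is 90% or 95%, and 5.7% to 28.6% when *o* is 50%.

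**Step 3: can the direction reverse?** Step 1 takes *o* as equal in both groups. A drain might empty a collection that CT would otherwise show, lowering *o* among drained patients to some *o₁*. With 75% found in undrained patients and *x* = 0.3, the bias vanishes when *o₁* + 0.3(1 − *o₁*) = 0.75, so *o₁* = 0.45/0.70 = 64%. With *x* = 0.8 no fall in *o₁* cancels it, since the drain alone would reveal 80%, more than 75%.

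**Step 4: what a restricted outcome achieves** (*p* = 0.05, *o* = 0.75).

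- *Dropping only leaks that met no other criterion.* Suppose drain effluent prompts a scan or reoperation that confirms 80% of the leaks the drain revealed. These stay in. The drained risk is 0.05 × (0.75 + 0.25 × *x* × 0.8), which is 0.0405 at *x* = 0.3 and 0.0455 at *x* = 0.8. The OR is still 1.08 to 1.22, against 1.10 to 1.28 unrestricted.
- *Also dropping leaks first signalled by the drain.* This can go too far. If, say, 20% of the leaks in drained patients that would have surfaced anyway show first in the drain, the drained risk is 0.05 × 0.75 × 0.8 = 0.030. The OR is (0.030/0.970)/(0.0375/0.9625) = 0.79.

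The all-leak and restricted results therefore err in opposite directions under these assumptions.

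**The case against.** **The size is assumed.** This stands. No detection share is in the protocol. Daily examination and outpatient follow-up to 6 weeks after discharge give undrained leaks time to surface. If 90% or more do so, the bias is small.

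**Sampling error may dominate.** This stands as a matter of proportion. With 531 patients per group and the 1.28 case, the expected events are 25.2 and 19.9, and the 95% interval is about 0.70 to 2.33. A wide interval does not remove a bias, but it limits how often the bias would mislead through a significance test.

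**Drainage is peripheral.** This stands in part. It is missing from the shorter list under Outcome measures, the title centres on the DULK score and the two serum markers, and Statistical Analysis does not say which covariates enter the model. Yet the protocol expressly names it a potential risk factor.

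**The criterion is a deliberate choice in line with usual practice.** This is granted. Background lists feculent and purulent drainage among common clinical signs. Nothing here argues for removing it from the outcome.

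**A sensitivity analysis belongs in the SAP.** The model could. The data behind it could not be recovered reliably: the protocol does not say that the criterion establishing each leak, or the order of signs, is recorded.

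Two stronger readings are tempting. A reader might infer that an odds ratio above 1 for drains must be spurious, or that a neutral drain is bound to show one. Step 3 shows why the documents do not support that. A reader might also infer that other factors, such as level of anastomosis, surgeon or open approach, inherit the bias. No passage links drain use to any of them, so that claim is not made.

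**Conclusion.** The point holds as a definitional overlap between exposure and outcome ascertainment that adjustment cannot remove. Upward bias in the drain odds ratio is likely but not proven. Its size is not determined by the protocol: illustratively 1.03 to 1.56 with no true effect, resting on 60% to 90% of leaks being found by the other criteria equally in both groups and drains revealing 30% to 80% of the rest. The consequence is confined to the odds ratio for drainage. The leak-rate definition is not called into question. The change is worth making because it is cheap and the information cannot be dependably rebuilt later.

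**What to change.** 1. Add to the CRF a tick-list of every criterion in the outcome definition that each leak met, and one item for which sign came first.
2. Keep the full definition for the leak rate and the main analyses.
3. For the drain odds ratio only, univariate and multivariate, show beside the all-leak result a sensitivity model that does not count leaks established by drain contents alone or first signalled by them. State that drain effluent by itself does not qualify as a departure from the expected recovery. Otherwise that criterion would bring these leaks back in and the restriction would do almost nothing.
4. Report the drain odds ratio as an association subject to detection bias, not as a causal effect, and read the two results as a range.

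The cost is a short CRF addition and one extra model. That model has fewer events and a wider interval. It may understate the drain odds ratio, because some leaks first seen in the drain would have surfaced anyway. The bias is reduced, not abolished. Nothing in patient care changes.
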